After the preceding procedures are completed, site personnel will undertake the following (infusion and post-infusion):

- Administer study medication (800 mg)
- Record vital sign measurements after the completion of the infusion and observe the patient for at least 15 minutes
- Record AEs

6.1.2 Events for Day 14 (± 1 day) and Weeks 4, 6, 8, 10, 14, 16, 18, 20, 22, 26, 28, 30, 32, 34, 38, 40, 42, 44, 46, 50, 52, 54, 56, 58, 62, 64, 66, 68, 70, 74, 76, 78, 80, 82, 84, 86, 88, 90, 92, 94, 98, 100, 102, 104, 106, 110, 112, 114, 116, 118, 122, 124, 126, 128, 130, 134, 136, 138, 140, and 142 (± 2 days)

The following will be completed before study drug administration:

- Record vital sign measurements
- Record AEs and concomitant medications
- Assess adherence to the OBR (Weeks 4, 8, and 84 only)
- Collect urine sample for the following:
Urine pregnancy test for females of childbearing potential (Weeks 4, 8, 16, 20, 28, 32, 40, 44, 52, 56, 64, 68, 76, 80, 84, 88, 92, 100, 104, 112, 116, 124, 128, 136, and 140 only)

Site personnel will undertake the following after administration of study drug (800 mg):

- Record vital sign measurements after completion of infusion and observe patient for at least 15 minutes
- Record AEs

6.1.3 Events for Weeks 12, 24, 36, 48, 60, 72, 96, 108, 120, 132, 144/EOS and 150/Follow-up (± 2 days)

The following will be completed before study drug administration:

- Record results of physical examination (complete exam at Weeks 24, 48, 72, 96, 120, 144, and 150; abbreviated exam at Weeks 12, 36, and 60)
- Record the patient's weight (Weeks 12, 24, 36, 48, 60, 72, 96, 120, 144 and 150 only)
- Record vital sign measurements

- Record AEs and concomitant medications
- Assess adherence to the OBR
- Collect blood and/or urine samples for the following:
 - Hepatitis serology and C-reactive protein (Weeks 24, 48, 96, and 150 only)
 - Clinical laboratory assessments (serum chemistry, hematology, and urinalysis; See [Section 7.2.2](#) for a complete list of parameters) (Weeks 12, 24, 36, 48, 60, 72, 96, 120, and 150 only)
 - Archive sample (Weeks 12, 24, 36, 48, 60, 72, 96, 120, 144, and 150 only)
 - Pregnancy test for females of childbearing potential (urine at Weeks 12, 36, 60, 108, 120, 132, 144, and 150 only); serum at Weeks 24, 48, 72, and 96 only)
 - HIV-1 RNA (viral load)
 - HIV-1 viral resistance sample (will be stored for later use if needed)
 - CD4⁺ cell count (within 1 hour before the start of the infusion)

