After the preceding procedures are completed, site personnel will undertake the following (infusion and post-infusion):

- Administer study medication (2,000 mg)
- Record vital sign measurements after the completion of the infusion and observe the patient for at least 15 minutes
- Record AEs

6.2.2 Events for Weeks 4, 8, 16, 20, 28, 32, 40, 44, 52, 56, 64, 68, 76, 80, 84, 88, 92, 100, 104, 112, 116, 124, 128, 136, and 140 (± 2 days)

The following will be completed before study drug administration:

- Assess adherence to the OBR (Weeks 4, 8, and 84 only)
- Record vital measurements
- Record AEs and concomitant medications
- Collect urine sample for the following:
Urine pregnancy test for females of childbearing potential

Site personnel will undertake the following after administration of study drug (2,000 mg):

- Record vital sign measurements after completion of infusion and observe patient for at least 15 minutes
- Record AEs

6.2.3 Events for Weeks 12, 24, 36, 48, 60, 72, 96, 108, 120, 132, , 144/EOS, and 150/Follow-up (± 2 days)

The following will be completed before study drug administration:

- Record results of physical examination (complete exam at Weeks 24, 48, 72, 96, 120, 144, and 150 only; abbreviated exam at Weeks 12, 36, and 60 only)
- Record the patient's weight (Weeks 12, 24, 36, 48, 60, 72, 96, 120, 144, and 150 only)
- Record vital sign measurements
- Record AEs and concomitant medications
- Assess adherence to the OBR
- Collect blood and/or urine samples for the following:
 - Hepatitis serology and C-reactive protein (Weeks 24, 48, 72, 96, and 150 only)

-
- Clinical laboratory assessments (serum chemistry, hematology, and urinalysis; See [Section 7.2.2](#) for a complete list of parameters) (Weeks 12, 24, 36, 48, 60, 72, 96, 120, and 150 only)
 - Archive sample (Weeks 12, 24, 36, 48, 60, 72, 96, 120, 144, and 150 only)
 - Pregnancy test for females of childbearing potential (urine at Weeks 12, 36, 60, 108, 120, 132, 140, 144, and 150 only; serum at Weeks 24, 48, 72, and 96 only)
 - HIV-1 RNA (viral load)
 - HIV-1 viral resistance sample (will be stored for later use if needed)
 - CD4⁺ cell count (within 1 hour before the start of the infusion)
 - Immunogenicity of ibalizumab (Weeks 24, 48, 72, 96, 120, 144, and 150 only)

Site personnel will undertake the following after administration of study drug (2,000 mg) (not done at Week 150/Follow-up):

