6.3.3 Events for Day 7 (± 1 day)

Day 7 serves as the time point at which the antiviral activity of ibalizumab will be assessed to address the primary effectiveness objective of the study.

Site personnel will undertake the following:

- Assess adherence to the OBR
- Record results of abbreviated physical examination
- Record vital sign measurements, AEs, and concomitant medications
- Collect blood and urine samples for the following:
 - Clinical laboratory assessments (serum chemistry, hematology, and urinalysis; see [Section 7.2.2](#) for a complete list of parameters)
 - Archive sample
 - HIV-1 RNA (viral load)
 - HIV-1 viral resistance sample (will be stored for later use if needed)
 - CD4⁺ cell count

6.3.4 Events for Day 14 (± 1 day), and Weeks 4, 6, 8, 10, 14, 16, 18, 20, 22, 26, 30, 32, 34, 38, 40, 42, 44, 46, 50, 52, 54, 56, 58, 62, 64, 66, 68, 70, 74, 76, 78, 80, 82, 86, 88, 90, 92, 94, 98, 100, 102, 104, 106, 110, 112, 114, 116, 118, 122, 124, 126, 128, 130, 134, 136, 138, 140, and 142 (± 2 days)

The following will be completed before study drug administration:

- Record results of physical examination (complete exam at Week 4 only, abbreviated exam at Weeks 20, 32, and 40 only)
- Record the patient's weight (Weeks 4, 20, 32, and 40 only)
- Record vital sign measurements
- Record AEs and concomitant medications
- Assess adherence to the OBR (Weeks 4, 8, 20, 32, and 40 only)
- Collect urine and perform pregnancy test for females of childbearing potential (Weeks 4, 8, 16, 20, 32, 40, 44, 52, 56, 64, 68, 76, 80, 88, 92, 100, 104, 112, 116, 124, 128, 136, and 140 only)
- Collect blood samples for the following:
 - HIV-1 RNA (viral load) (Day 14, and Weeks 4, 6, 8, 16, and 20 only)
 - HIV-1 viral resistance sample (will be stored for later use if needed) (Day 14, and Weeks 4, 6, 8, 16, and 20 only)
 - CD4⁺ cell count (Day 14, and Weeks 4, 6, 8, 16, and 20 only)

Site personnel will undertake the following after administration of study drug (800 mg):

- Record vital sign measurements after completion of infusion and observe patient for at least 1 hour; if the patient did not experience an AE(s) related to the infusion (local or systemic) through and including the infusion on Day 14, then the observation time can be reduced to 15 minutes
- Record AEs

6.3.5 Events for Weeks 12, 24, 48, 60, 72, 84, 96, 108, 120, 132, and 144/EOS (± 2 days)

Site personnel will undertake the following before administration of study drug:

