6.4 Early Withdrawal Procedures

Patients who withdraw from the study at any time before Week 96/EOS will be asked to complete all Early Withdrawal procedures to ensure safety and collect as much effectiveness data as possible.

The following procedures will be completed at the Early Withdrawal visit (study drug is not administered at Early Withdrawal):

- Record results of a complete physical examination
- Record the patient's weight
- Record vital sign measurements

- Record AEs and concomitant medications
- Assess adherence to the OBR
- Collect blood and/or urine samples for the following:
 - Hepatitis serology and C-reactive protein
 - Clinical laboratory assessments (serum chemistry, hematology, and urinalysis; see [Section 7.2.2](#) for a complete list of parameters)
 - Archive sample
 - Serum pregnancy test for females of childbearing potential
 - HIV-1 RNA (viral load)
 - HIV-1 viral resistance sample (will be stored for later use if needed)
 - CD4⁺ cell count
 - Immunogenicity of ibalizumab

6.5 **Unscheduled Visits**

Unscheduled visits are allowed for the following reasons:

- To perform a confirmatory plasma viral load determination
- To perform confirmatory laboratory testing for clinically abnormal values
- Any time the investigator feels that they are clinically required for safety reasons related to the patient's participation in this trial

Findings during these unscheduled visits must be reported in the EDC system under the unscheduled visit section.

7. Study Assessments

A central laboratory will analyze all blood and urine samples with the exception of the HIV-1 resistance testing and immunogenicity testing, which will be undertaken by appropriate specialty contract laboratories. Urine samples will be analyzed at the site; if abnormal results are obtained for a patient, a urine sample will be sent to the central laboratory for microscopic evaluation.

The following assessments will be conducted at the times indicated in the Schedule of Events (Tables 3-1 through 3-6).

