For Cohort 2, patients will complete all screening procedures during the six weeks before Baseline/Day 0. Successful screening results will allow the patients to proceed to the Baseline/ Day 0 Visit, where they will initiate the selected OBR in addition to undergoing physical and laboratory measures. At this visit patients will also receive the loading dose of the study medication (2000 mg). Patients will return to the clinic on Day 7 for effectiveness and safety evaluations, and on Day 14 and every two weeks thereafter through the remainder of participation in the study (up to 144 weeks) for study drug administration (800 mg) and effectiveness and safety evaluations. Patients who are discontinued or who withdraw from the study prematurely will be asked to return for an Early Withdrawal visit to have all assessments detailed in the Schedule of Events for that visit performed.

All patients who complete Week 144 or end of study (EOS) visit will return for a follow-up visit at Week 150. Patients may be discontinued from the study at the patient's request or if the patient becomes pregnant, at investigator request, for a protocol violation, for treatment-related serious or intolerable adverse events (AEs), for toxicity (defined as two consecutive laboratory results, at least 14 days apart, with a CD4+ T-cell count below 200 cells/mm3 that also represents a 50% reduction from the Baseline CD4+ T-cell count), or for virologic failure. Virologic failure is defined as two consecutive measurements beginning at Week 24 or later if less than a 0.5 log10 decline from the Baseline viral load.

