## **Breakthrough:**

Patient has suppressed viral load (< 50 copies) at any time after primary endpoint followed by ≥200 copies at two consecutive scheduled efficacy assessments.

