## **Virologic Suppression:**

Patient has a  $\ge 0.5 \log_{10}$  decline and does suppress (< 50 copies) at any time after primary endpoint and does not have a  $\ge 1 \log_{10}$  increase from nadir on any two consecutive scheduled efficacy assessments after achieving the  $\ge 0.5 \log_{10}$  decline from BL.

A table summarizing virologic outcome at the each key visit after Week 12 [Weeks 24, 48, 72, 96, 120, and 144/EOS] according to the above categories will be provided. A listing indicating the virologic outcome for each patient will be included.

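### Cohort 1 has no viral load, resistance or CD4 sample at Week 84, so the Week 96 outcome categories that need two consecutive scheduled values are not comparable with Cohort 2 or with other key visits

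*Protocol*

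**What the plan says.** **Cohort 1.** In the 800 mg schedule (protocol 6.1.3 and Table 3-2), viral load, stored resistance sample and CD4 are taken at "Events for Weeks 12, 24, 36, 48, 60, 72, 96, 108, 120, 132, 144/EOS and 150/Follow-up". The 2,000 mg schedule (6.2.3 and Table 3-4) uses the same weeks: "Events for Weeks 12, 24, 36, 48, 60, 72, 96, 108, 120, 132, , 144/EOS, and 150/Follow-up". Week 84 is an infusion visit in both. Beyond the routine infusion-visit items it has only a urine pregnancy test and the background-regimen question: "Assess adherence to the OBR (Weeks 4, 8, and 84 only").

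**Cohort 2.** Section 6.3.5 and Table 3-6 include Week 84: "Events for Weeks 12, 24, 48, 60, 72, 84, 96, 108, 120, 132, and 144/EOS". All three samples are taken there.

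**Analysis.** SAP 4.5.2 extends every secondary efficacy endpoint to all cohorts, and SAP 3.4.1 displays the groups side by side with a total. Under SAP 4.5.2.3, Breakthrough requires at least 200 "copies at two consecutive scheduled efficacy assessments" after suppression. Rebound likewise needs two consecutive scheduled visits. Suboptimal Response and Virologic Suppression are defined partly by the absence of two consecutive rises of at least 1 log10 from nadir. The SAP then promises "A table summarizing virologic outcome at the each key visit after Week 12", meaning Weeks 24, 48, 72, 96, 120 and 144.

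**Protocol-defined failure** is separate and is not tied to scheduled visits: "Virologic failure is defined as two consecutive measurements beginning at Week 24 or later". Protocol 6.5 permits an unscheduled visit "To perform a confirmatory plasma viral load determination".

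**The concern.** A category that needs two consecutive scheduled values depends on the spacing of those values. At Week 96 the two latest Cohort 1 values are from Weeks 72 and 96. In Cohort 2 they are from Weeks 84 and 96.

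Take a patient below 50 copies/mL at Week 72, say at a nadir of 40, whose viral load from Week 80 onward is at least 400. That is a rise of log10(400/40) = 1.0 from nadir. Suppose the value also stays at least 0.5 log10 below Baseline. In Cohort 2 there are two qualifying values by Week 96, so the patient is Breakthrough and is excluded from Virologic Suppression. In Cohort 1 there is one qualifying value, so the patient is not Breakthrough and still fits Virologic Suppression at Week 96. A difference between cohorts in that row, or a change from Week 72 to 96 to 120 within Cohort 1, would partly reflect the sampling calendar.

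Two further losses follow. Resistance testing relies on stored samples from patients who fail, and a Week 84 sample that was never drawn cannot be recovered. The two-result CD4 toxicity definition has no scheduled input between Weeks 72 and 96. Under the SAP's carry-forward rule, a missing Week 96 CD4 count would be filled from Week 72.

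**Working it through.** The plan states no figure on this point, so there is none to reproduce.

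**Inputs (Tables 3-1 to 3-6).** Scheduled viral load weeks from Week 12:
- Cohort 1, both doses: 12, 24, 36, 48, 60, 72, 96, 108, 120, 132, 144, then 150 off drug.
- Cohort 2: 12, 16, 20, 24, 28, 36, 48, 60, 72, 84, 96, 108, 120, 132, 144, then 150 off drug.

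**Assumptions.** Failure is persistent, onset is uniform over the 24 weeks before key visit k, and classification at k uses data up to k only.

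**Share confirmable at k.** Two scheduled values must fall between onset and k, so onset must be no later than the preceding sample p. Share = (p − (k − 24)) / 24.

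| Key visit | Cohort 1: p, share | Cohort 2: p, share |
|---|---|---|
| 24 | 12, 12/24 = 50% | 20, 20/24 = 83% |
| 48 | 36, 50% | 36, 50% |
| 72 | 60, 50% | 60, 50% |
| 96 | 72, 0/24 = 0% | 84, 50% |
| 120 | 108, 50% | 108, 50% |
| 144 | 132, 50% | 132, 50% |

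The unconfirmable window before Week 96 is 96 − 72 = 24 weeks in Cohort 1, against 96 − 84 = 12 weeks in Cohort 2.

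**Delay to the second scheduled value, onset uniform over Weeks 72 to 96.**
- Without Week 84, the second value is always Week 108: mean 108 − 84 = 24 weeks, range 12 to 36.
- With Week 84, onsets in 72–84 are confirmed at Week 96 (mean 96 − 78 = 18) and onsets in 84–96 at Week 108 (mean 108 − 90 = 18): overall mean 18 weeks, range 12 to 24.

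**Does the Week 96 response status change?** Take S as at least a 0.5 log10 decline and F as less, at Weeks 72, 84 and 96. Assume response at Week 60, and apply the SAP rule that visits after a confirmed failure are set to failure.

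| Pattern | Response at 96: without / with Week 84 | Confirmed by 96: without / with Week 84 |
|---|---|---|
| SSS | yes / yes | no / no |
| SSF | no / no | no / no |
| SFS | yes / yes | no / no |
| SFF | no / no | no / **yes** |
| FSS | yes / yes | no / no |
| FSF | no / no | **yes** / no |
| FFS | yes / **no** | no / **yes** |
| FFF | no / no | yes / yes |

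For patients responding at Week 72 (first four rows), Week 96 response is identical under both schedules. Only SFF differs, and only in confirmation. FFS changes response status, but that failure had begun by Week 72. FSF goes the other way, because Weeks 72 and 96 become consecutive when Week 84 is absent.

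**Illustration.** The documents give no failure rate. If 2%, 5% or 10% fail persistently per 12 weeks, the confirmed categories at Week 96 would miss about 2, 5 or 10 percentage points that a Week 84 sample would confirm. Single-value failure at Week 96 is 1 − (1 − r)² = 4.0%, 9.8% or 19.0% under either schedule.

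**The case against.** A reader might infer that Week 96 results in Cohort 1 look better by construction. The documents do not support that. The below-50 and below-400 proportions, the 0.5 and 1.0 log10 response proportions, mean change, snapshot category 2a and the CD4 summaries all use the Week 96 value, and a missing viral load counts as failure. The FSF pattern also shows that the effect is not strictly one-directional.

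A reader might also infer that no failure in Weeks 72 to 96 can be confirmed at all. That is too strong. Protocol-defined failure does not require scheduled visits, and unscheduled confirmatory draws are allowed. Such draws do not count toward categories worded in terms of scheduled assessments, however, and with nothing sampled between Weeks 72 and 96 there is little to prompt one.

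Other objections stand in part:
- Text and tables agree for both dose groups, so an oversight is not established. At Weeks 108 and 132 physical examination, weight and safety laboratory tests are dropped while virology and CD4 are kept, so Week 84 breaks the pattern. No reason is given.
- The SAP does not say whether values after a key visit are ignored. If later values are used, Week 108 supplies the confirmation.
- The categories overlap anyway. A move from 40 to 300 copies/mL (0.88 log10) meets both Breakthrough and Virologic Suppression in either cohort, and a Week 84 sample does not cure that.
- The failure-to-maintain category does not clearly demand two failing values, so some patients who lose the 0.5 log10 decline at Week 96 might be placed there on one value.
- The cohorts also differ at Week 24 (83% against 50%), so restoring Week 84 does not make the table comparable throughout.

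**Conclusion.** The gap is real in both Cohort 1 dose groups. It affects the SAP's other virologic outcomes at Week 96: Breakthrough, Rebound, and the success categories defined by the absence of two consecutive rises. Those rows are not comparable with Cohort 2 at Week 96 or with Cohort 1's other key visits. The size is 0% against 50% confirmable, and a mean confirmation delay of 24 against 18 weeks. Both figures rest on persistent failure and uniform onset, and the first also on using data up to the key visit only. Even with a Week 84 sample, the last 12 weeks before Week 96 would stay unconfirmable. The gap doubles that window rather than creating it.

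Which key visit is affected depends on week numbering. A SAP listing footnote puts end of study at Week 174 for TMB-301 rollovers and Week 150 for others, a difference of 24 weeks. If that group is analysed on cumulative weeks, its gap runs from Week 96 to Week 120, and Week 120 is the affected key visit. The SAP does not settle this.

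Severity is minor. Cohort 1 efficacy is not a protocol effectiveness endpoint. The SAP adds it for completeness, as descriptive secondary analysis without formal testing.

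**What to change.** 1. Add HIV-1 RNA, the stored resistance sample and CD4 to the existing Cohort 1 Week 84 infusion visit in Tables 3-2 and 3-4, and amend sections 6.1 and 6.2 to match. If the omission was intended, state the reason. The cost is one extra blood draw at a visit that already takes place, plus the assays.
2. For patients already past Week 84, footnote the Week 96 confirmed-outcome table as not comparable across cohorts or visits. Add a sensitivity version, in all cohorts, in which the Week 108 value confirms a failure seen at Week 96. The cost is SAP wording and a 12-week wait for confirmation.
3. Do not extend forward confirmation to Week 144. The next scheduled value there is Week 150, when no drug is given. State how patients with no later value, such as early discontinuers, are handled.
4. State in SAP 4.5.2.3 whether values after a key visit may be used, and whether TMB-301 rollovers are analysed on cumulative weeks. If they are, move their footnote and sensitivity analysis to Week 120, confirmed at cumulative Week 132 (108 + 24).

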6.2 Cohort 1: 2,000 mg Every 4 Weeks

Since there are no laboratory parameters required for entry into Cohort 1 of this study, Screening procedures and Day 0 procedures are scheduled for the same day. Patients who qualify for entry into Cohort 1 of this study who are currently receiving 2,000 mg ibalizumab every 4 weeks will have physical and laboratory measures performed and will receive the first on-study dose of ibalizumab at Screening/Day 0, as specified in the Schedule of Events (see Table 3-3). These patients will return to the clinic at Week 4 and every 4 weeks thereafter through the remainder of participation in the study

for study drug administration (2,000 mg) and effectiveness and safety evaluations. Patients who are discontinued or who withdraw from the study prematurely will be asked to return for an Early Withdrawal visit to have all assessments detailed in the Schedule of Events for that visit performed.

6.2.1 Screening/Day 0

Screening and Day 0 (first on-study administration of ibalizumab) are scheduled for the same day. At this visit, study information will be reviewed and discussed, and the participant will review and sign the informed consent form. No procedures, other than a preliminary verbal assessment of eligibility by review of inclusion/exclusion criteria, may be done before the informed consent process is complete. Once informed consent has been obtained and documented, the following procedures may be completed (pre-infusion):

- Record demographics, medical history (general and HIV), and the patient's height
- Record all prior ART exposure; record all other medications taken within the last 30 days
- Record results of a complete physical examination
- Record vital sign measurements
- Record the patient's weight
- Record AEs that begin after the patient signs the informed consent (see [Section 8.1](#) for definitions)
- Collect blood and urine for the following laboratory samples:
 - Hepatitis serology and C-reactive protein
 - Clinical laboratory assessments (serum chemistry, hematology, and urinalysis; see [Section 7.2.2](#) for a complete list of parameters)
 - Archive sample
 - Serum pregnancy test in females of childbearing potential and an FSH test in postmenopausal females
 - HIV-1 RNA (viral load)
 - HIV-1 viral resistance sample (will be stored for later use if needed)

- CD4⁺ cell count (within 1 hour before the start of the infusion)
- Immunogenicity of ibalizumab

After the preceding procedures are completed, site personnel will undertake the following (infusion and post-infusion):

- Administer study medication (2,000 mg)
- Record vital sign measurements after the completion of the infusion and observe the patient for at least 15 minutes
- Record AEs

6.2.2 Events for Weeks 4, 8, 16, 20, 28, 32, 40, 44, 52, 56, 64, 68, 76, 80, 84, 88, 92, 100, 104, 112, 116, 124, 128, 136, and 140 (± 2 days)

The following will be completed before study drug administration:

- Assess adherence to the OBR (Weeks 4, 8, and 84 only)
- Record vital measurements
- Record AEs and concomitant medications
- Collect urine sample for the following:
Urine pregnancy test for females of childbearing potential

Site personnel will undertake the following after administration of study drug (2,000 mg):

- Record vital sign measurements after completion of infusion and observe patient for at least 15 minutes
- Record AEs

6.2.3 Events for Weeks 12, 24, 36, 48, 60, 72, 96, 108, 120, 132, , 144/EOS, and 150/Follow-up (± 2 days)

The following will be completed before study drug administration:

- Record results of physical examination (complete exam at Weeks 24, 48, 72, 96, 120, 144, and 150 only; abbreviated exam at Weeks 12, 36, and 60 only)
- Record the patient's weight (Weeks 12, 24, 36, 48, 60, 72, 96, 120, 144, and 150 only)
- Record vital sign measurements
- Record AEs and concomitant medications
- Assess adherence to the OBR
- Collect blood and/or urine samples for the following:
 - Hepatitis serology and C-reactive protein (Weeks 24, 48, 72, 96, and 150 only)

-
- Clinical laboratory assessments (serum chemistry, hematology, and urinalysis; See [Section 7.2.2](#) for a complete list of parameters) (Weeks 12, 24, 36, 48, 60, 72, 96, 120, and 150 only)
 - Archive sample (Weeks 12, 24, 36, 48, 60, 72, 96, 120, 144, and 150 only)
 - Pregnancy test for females of childbearing potential (urine at Weeks 12, 36, 60, 108, 120, 132, 140, 144, and 150 only; serum at Weeks 24, 48, 72, and 96 only)
 - HIV-1 RNA (viral load)
 - HIV-1 viral resistance sample (will be stored for later use if needed)
 - CD4⁺ cell count (within 1 hour before the start of the infusion)
 - Immunogenicity of ibalizumab (Weeks 24, 48, 72, 96, 120, 144, and 150 only)

Site personnel will undertake the following after administration of study drug (2,000 mg) (not done at Week 150/Follow-up):

- Record vital sign measurements after completion of infusion and observe patient for at least 15 minutes
- Record AEs

6.3 Cohort 2

Patients will complete all Screening procedures during the 6 weeks before Day 0/Baseline. Successful Screening results will allow the patients to proceed to the Day 0/Baseline visit, where they will initiate the selected OBR in addition to undergoing physical and laboratory measures as specified in the Schedule of Events (see Table 3-5). At this visit, patients will also receive the loading dose of the study medication (2,000 mg). Patients will return to the clinic on Day 7 for effectiveness and safety evaluations and on Day 14 and every 2 weeks thereafter through the remainder of participation in the study for study drug administration (800 mg) and effectiveness and safety evaluations. Patients who are discontinued or who withdraw from the study prematurely will be asked to return for an Early Withdrawal visit to complete all assessments for that visit, as detailed in the Schedule of Events.

